# 8) Risks to Subjects\*

## tDCS risks and safety plan

The risks associated with tDCS are minimal. There is no documented risk of seizure associated with tDCS, but participants with a history of seizure disorder will be excluded to ensure optimum safety. Side effects associated with tDCS include mild headache, tingling, itching, or stinging under the electrodes, and skin irritation. After each therapy session, an aloe cream will be applied to the skin under the electrodes to reduce risks associated with skin drying.

#### **Balance training and safety plan**

There is a small risk that balance training cause injury during balance training, but participants may feel mild muscle soreness during and after balance training activities. For the safety of participants, all exercise sessions will be supervised by a certified athletic trainer. If participants perform an activity in a way that may hurt them, they can take a rest anytime they want, and we will demonstrate a proper form of exercise.

## TMS risks and safety plan

TMS is a safe procedure that has been used on many people to study the brain. Most people do not find the stimulation painful, but occasionally strong contractions of scalp muscles can cause some discomfort or headache. TMS-induced headaches are mild and brief (less than 1 hour).

If a headache or mild scalp discomfort occurs, subjects will be directed to use over the counter pain medication at their own discretion. The symptoms usually go away promptly with nonprescription medication.

The noise of the TMS magnet may affect hearing, so subjects will be required to wear disposable earplugs during TMS session.

The risk of inducing a seizure with single-pulse TMS\* is considered very low. Seizures from single-pulse TMS have only been reported in subjects with medicallyintractable epilepsy very rarely (0.0-3%).

In the unlikely event of a seizure, a standard seizure protocol will be followed.

- 1. First thing: REMOVE THE COIL FROM SUBJECT'S BRAIN
- 2. Remove harmful objects from the subject's surrounding area
- 3. Cushion the head as possible and the area so subject does not injure themselves
- 4. If the subject is having trouble breathing, turn the subject on their side
- 5. Monitor the duration of the seizure

6. If the seizure ends in less than 60 seconds, monitor and contact primary care doctor to rule out predisposing factors

7. If seizure lasts more than 60 seconds, activate emergency services.

#### Precautions:

Do not place anything or any fingers anywhere near the mouth Do not attempt to hold the subject down Remain calm, seizures almost always stop after a few minutes

TMS can interfere with implanted medical devices and will not be done in people who have pacemakers, implanted pumps, or stimulators, such as cochlear implants or in people who have metal objects inside the eye or skull. All participants will be screened before enrollment to assure that they meet study criteria and that there are no contraindications to TMS, subjects will be instructed that they can discontinue the TMS experiment at any time

\* The amount of energy introduced to the body is considered safe. The duration of the stimulus is extremely brief (less than 1 millisecond) and the maximum intensity is 1.4 Tesla (less than magnetic resonance imaging). The magnetic stimulation in this study feels similar to a gentle tap on the head. Please note the proposed study will utilize the single-pulse TMS that has been considered safer than other types of TMS techniques such as paired-pulse or repetitive TMS. FDA has approved repetitive TMS to treat depression.

## H-reflex and M-response risks and safety plan

H-reflex and M-response are also considered a safe procedure that has been used on many people to study the peripheral nerves. Most people do not find the stimulation painful, but occasionally strong contractions of tested muscles can cause some discomfort or pain. Stimulation-induced pain is mild and short (less than 4 hours). The pain is usually manageable with nonprescription pain medication.

\*\* The amount of energy introduced to the body is not significant. The duration of the stimulus is extremely brief (1 millisecond) and the maximum intensity is 200V. The shocks in this study feel like a shock of static electricity, like when you are walking across a carpet and then touch a door knob, except the voltage is much lower (A shock of static electricity can provide up to thousands of volts of electricity).

## 9) Potential Benefits to Subjects\*

There will be no guarantee of a specific benefit to individual participants; however, successful completion of this study will open a new class of therapeutic approaches for individuals with chronic ankle instability.

# 10) Vulnerable Populations\*

N/A

## 11) Setting

Data collection will take place at the Sports Medicine and Motion Analysis Laboratory at University of Miami.

## 12) **Resources Available**

All necessary equipment is available in the Sports Medicine and Motion Analysis Laboratory, and the investigators have considerable experience to safely conduct the proposed study.

## 13) **Prior Approvals**

This project has been approved by the Department of Kinesiology and Sports Sciences in the School of Education as a dissertation research project.

## 14) **Recruitment Methods**

Subjects will be recruited from the University of Miami's Medical and Coral Gables campuses as well as community centers and local sports medicine and orthopedic clinics. Flyers and emails approved by the University of Miami's Institutional Review Board (IRB) for the Use and Protection of Human Subjects will be used when permitted. We will be seeking permission to send an email to potential people by identifying in-charge person/officer in each university unit (i.e., departments, club sports teams, athletics) or building, who can provide us with a list of email addresses or can send an email for us. We will do the same for other places outside the university community.

## 15) Local Number of Subjects

Sixty human subjects with chronic ankle instability will be recruited and enrolled in the study. A statistical power analysis was performed to estimate sample size, based on the previous tDCS study [40] on CAI patients with similar dependent variables (e.g., corticospinal excitability). The effect size (f=0.55) in this study was large using Cohen's criteria. With an alpha=0.05 and power = 0.80, the projected sample size needed is approximately 8 participants for each group with a total of 24 CAI patients. Thus, the proposed sample size of 20 for each group with a total of 60 CAI patients will be more than adequate and should also allow for expected attrition.

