# 4) Inclusion and Exclusion Criteria\*

Below are characteristics of the subject population

- Anticipated number: 60 human subjects with chronic ankle instability
- Age: 18-45
- Sex: Both
- Race: All

Criteria for inclusion:

- Subjects should be neurologically sound.
- Subjects should have abilities to maintain single leg stance at least for 10 seconds.
- A history of ankle sprain
- A history of ankle joint giving ways
- Current feelings of ankle joint instability

Criteria for exclusion:

- Individuals with a clinically defined neurological disorder, with an increased risk of seizure for any reason, with a history of treatment with TMS, deep brain stimulation for any disorder will be excluded.
- Patients with cardiac pacemakers, implanted medication pumps, intracardiac lines, or acute, unstable cardiac disease, with intracranial implants (e.g. aneurysm clips, shunts, stimulators, cochlear implants, or electrodes) or any other metal object within or near the head, excluding the mouth, that cannot be safely removed will be excluded.
- A history of balance or vestibular disorder
- A history of previous surgeries to the musculoskeletal structures in either limb of the lower extremity
- A history of a fracture in either limb of the lower extremity requiring realignment

- A history of acute injuries to the lower extremity joints in the previous 3 months, which impacted joint integrity and function (i.e., sprains, fractures) resulting in at least 1 interrupted day of desired physical activity
- A history of herniated disc
- Poorly controlled headache
- Hypersensitivity to electrical or magnetic stimulation

The study will not recruit any of the special classes of subjects as shown below.

- Adults unable to consent
- Individuals who are not yet adults (infants, children, teenagers)
- Pregnant women
- Prisoner

[figure not shown]

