# 5) **Procedures Involved\***

## **Study Overview**

The proposed study is a double-blinded, randomized-control design which examines the efficacy of tDCS with balance training (BT) for patients with chronic ankle instability (CAI). Participants will be randomly allocated to one of two groups including (1) anodal tDCS + BT and (2) sham tDCS + BT. Outcome measures allow us to measure effects on postural balance, neural functions, and self-reported physical function.

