#### **Study Interventions**

Transcranial Direct Current Stimulation: Participants in the active and sham tDCS groups will receive tDCS while performing balance exercises (about 20-min application). An anodal surface electrode will be attached to the contralateral motor cortex (M1) of the CAI-involved side and the reference electrode will be placed on the ipsilateral side of the supraorbital ridge. These electrode placements (stimulation sites) were consistent with previous studies.[39, 40] Anodal tDCS will deliver a low electrical current stimulation at 2 mA, while for sham tDCS, the stimulator will be turned off automatically 30 s following the application. The sham stimulation mimics the transient scalp sensation perceived when the stimulator is initially switched on. This technique is currently state-of-the-art for conducting convincing sham stimulation in the tDCS field. For tDCS treatment set-up, participants will sit on the chair. Sponge electrodes will be placed and secured with a head strap: Active electrode over the motor cortex area and the reference electrode on the contralateral side of the upper forehead. The tDCS set-up will take approximately 10 minutes. Participants will undergo 12 sessions (20-min each) of active or sham tDCS using 2mA current. This constant current device ramps up to the desired amplitude and ramps the amplitude back to 0mA at the end of the treatment duration. tDCS (real or sham) will be delivered from beginning of balance training to the end of the training. After each training session, an aloe cream will be applied to the skin under the electrodes to reduce risks associated with skin drying. **Balance training:** All groups will receive the same progressive balance training (BT). BT will be implemented 3 times a week over 4 weeks, each training session lasting about 20 minutes. The 4 weeks of BT has been shown effective in enhancing postural control in patients with CAI. The BT will consist of 3 types of balance exercises: (A) single-leg stance exercise with eyes open and closed and on stable and unstable surfaces, (B) single-leg deadlift exercise with eves open and on stable and unstable surface, and (C) balance

exercise on wobble board. Participants will be asked to perform a progressive level of exercise in each session.

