# 7) Data Management\*

Data will be stored in a personal computer which is in locked research offices and is encrypted and password protected. The means and standard deviations will be calculated for one pre and two post outcome measures and will be used for statistical analysis. The normal distribution of data will be assessed by using the Shapiro-Wilk tests. For each outcome measures (postural control, neural measures, and self-

> reported function), 2 (group: anodal tDCS+BT and sham tDCS+BT) by 3 (time: preintervention, 2 weeks post-, 4 weeks post-intervention) ANOVA with repeated measures will be performed to determine effects of tDCS for each outcome measure. In the presence of a significant group-by-time interaction, a post-hoc analysis using Sidak adjustment will be conducted. The level of significance will be set a priori at 0.05. All statistical analyses will be performed using SPSS 26.0 statistical software (SPSS Incorporated, Chicago, IL, USA).

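### The sample-size section's per-group and total figures (8 and 24; 20 and 60) fit only three groups, but the trial has two

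*Combined protocol and SAP*

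**What the plan says.** Section 15 (Local Number of Subjects) opens with the enrolment target: "Sixty human subjects with chronic ankle instability will be recruited and enrolled in the study". From an effect size of f = 0.55, attributed to an earlier tDCS study in the same condition, with alpha 0.05 and power 0.80, it concludes that "the projected sample size needed is approximately 8 participants for each group with a total of 24 CAI patients". It then describes "the proposed sample size of 20 for each group with a total of 60 CAI patients" as more than adequate, with room for attrition. Section 4 repeats the total: "Anticipated number: 60 human subjects with chronic ankle instability".

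The design is described elsewhere with two groups:

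- Study Overview (section 5): "Participants will be randomly allocated to one of two groups", namely anodal tDCS with balance training and sham tDCS with balance training.
- Study Interventions (section 5): "Participants in the active and sham tDCS groups will receive tDCS while performing balance exercises".
- Section 7 (Data Management) plans a repeated-measures ANOVA of the form "2 (group: anodal tDCS+BT and sham tDCS+BT) by 3 (time: preintervention, 2 weeks post-, 4 weeks post-intervention".

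**The concern.** Each pair in section 15 should satisfy total = number of groups x size per group. Neither does for two groups, and both do for three. At least one figure in each pair is therefore wrong for this trial.

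Two things depend on it. The first is the arm size used to set up randomisation and to judge when recruitment is complete: 30 or 20 per arm. The second is whether the required number was worked out for the two-arm trial being run or for some other design. Section 15 is the only justification of sample size in the documents.

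**Working it through.** **Inputs.** From section 15: 8 per group and 24 in total; 20 per group and 60 in total; f = 0.55; alpha 0.05; power 0.80. From Study Overview and section 7: k = 2 groups. From section 7: m = 3 times. No allocation ratio is stated; equal arms are assumed, which fits a single size given for each group.

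**Step 1: group arithmetic.**

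| | Section 15 | Implied groups | Two arms, per-group figure kept | Two arms, total kept |
|---|---|---|---|---|
| Required | 8 and 24 | 24/8 = 3 | 2 x 8 = 16 | 24/2 = 12 per arm |
| Planned | 20 and 60 | 60/20 = 3 | 2 x 20 = 40 | 60/2 = 30 per arm |

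**Step 2: where could 24 come from?** Section 15 names no test and no correlation, so I tried several noncentral F calculations, with N the total and sphericity assumed for the interaction.

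*Group-by-time interaction*, df = (k-1)(m-1) and (N-k)(m-1), noncentrality f² x N x (m-1):

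- Three groups, N = 24: 0.3025 x 24 x 2 = 14.52, power 0.836. At N = 21, power is 0.769. The smallest balanced total is 24, or 8 per group, which reproduces the plan's pair exactly.
- Two groups, same formula: N = 16 gives 0.755 and N = 18 gives 0.811. The smallest balanced total is 18, or 9 per arm.

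*Between-group effect averaged over three times*, df = k-1 and N-k, noncentrality f² x N x m/(1 + (m-1) x rho):

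- Two groups, assumed rho = 0.7: at N = 24, 0.3025 x 24 x 3/2.4 = 9.075, power 0.821; at N = 22, power 0.783. The smallest balanced total is again 24, but that is 12 per arm.

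A three-group calculation reproduces both 8 and 24. A two-group calculation can reproduce 24 but then contradicts 8. The documents do not decide between them, so a three-group origin is a plausible inference and no more.

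**Step 3: is the planned size adequate?** For a two-group comparison at a single time, df = 1 and N-2, noncentrality f² x N:

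| Total N | Noncentrality | Power |
|---|---|---|
| 16 | 4.84 | 0.535 |
| 28 | 8.47 | 0.79994 |
| 30 | 9.075 | 0.828 |
| 40 | 12.10 | 0.924 |
| 60 | 18.15 | 0.987 |

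This has the lowest power of the three tests shown. The two-group interaction in Step 2 gives 0.994 at N = 40. At f = 0.55, both 40 and 60 are enough.

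**The case against.** The mismatch itself is hard to explain away. Unequal allocation fails because one size is given for each group. Attrition fails because 24 is the requirement before any allowance, and both pairs carry the same factor of 3. A single mistyped digit cannot produce the same factor twice.

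The better objections concern remedy and weight.

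- **Preference for 60.** If the numbers were carried over from a three-group plan, then 60 = 3 x 20 was carried over too, and its repetition in section 4 is not independent support. This stands in part: 60 is the only total stated as the enrolment target, which favours 30 per arm, but 40 is not excluded and the sponsor must confirm.
- **Traces of another design.** The Background hypothesises superiority to balance training alone, and Study Interventions speaks of all groups. Neither creates a third arm against the explicit two-group wording. Figure 1, the study flowchart, is not in the text available to me, so the absence of a third arm is established from the text only.
- **Choice of power formulas.** The two-group match to 24 needs an assumed correlation: 0.7 and 0.75 give 24, but 0.65 gives 22 and 0.8 gives 26. Another common interaction form, with noncentrality f² x N x m/(1-rho), needs only 8 in total at rho = 0.5 and 6 at rho = 0.7. This stands: the required totals are illustrations. The contradiction in the group arithmetic does not depend on them.
- **Little harm.** Power is adequate at f = 0.55 on either reading. This stands and limits the severity, although an enrolment target uncertain by 20 people is more than a matter of wording.

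**Conclusion.** The concern holds. The required and planned sample sizes in section 15 are each inconsistent with the two-arm design as randomised, treated and analysed. Assuming equal arms, the planned size is 30 per arm (total 60) or 20 per arm (total 40), and the stated requirement is 16 or 24 in total. The documents do not settle which figures are wrong; 60 with 30 per arm is the better-supported reading.

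At the plan's own f = 0.55 the trial is not underpowered on either reading, so the harm is confined to a sample-size statement that is wrong as written and a requirement that cannot be traced to the planned test. That conclusion is conditional on f = 0.55, which was taken as given and not assessed here. This should be fixed, but it does not threaten the trial.

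**What to change.** Restate section 15 for two arms:

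1. State one total and the matching number per arm. If the enrolment target stands, that is 60 in total and 30 per arm. The sponsor should confirm that 20 per arm (40 in total) was not intended.
2. Replace the requirement of 8 per group and 24 in total with one computed for the planned 2 x 3 group-by-time test. Name the test and give the correlation, sphericity and attrition assumptions so that it can be reproduced.

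Cost: if 60 is confirmed, only the wording of section 15 changes. If 40 was intended, the totals in sections 4 and 15 change as well. Provided the sponsor confirms two arms, the allocation and the planned analysis stay as they are, and no additional patients are needed in either case.

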## 16) **Confidentiality**

All collected data will be kept in a locked cabinet at the laboratory (Room 123 in the Max Orovitz, [name]). Only the principal researcher and his research staff will be allowed access. All electronic data will be stored in a password-locked computer that is kept in the locked cabinet, and only the principal researcher and his research staff will have the password. All records will be identified using only ID numbers and no information than may reveal the subject's identity will be attached to these records. The ID list and the signed consent forms will be kept in a separate locked cabinet in the room 120, only accessible by the principal researcher.

## 17) **Provisions to Protect the Privacy Interests of Subjects**

All interactions will be limited to the principal investigator and study team.

## 18) **Consent Process**

A signed informed consent form will be required from all subjects participating in the study. The consent form will be in plain language and describe all aspects of the study: the purpose, procedure, time requirements, and any potential risk factors associated with participation. Informed consent will be obtained from subjects upon during the first visit to the lab (University of Miami, Coral Gables). Informed consent will be reviewed by the subject and explained by researcher. This will include answering any questions the subject has. The PI will obtain consent.

